9.7 Adverse Event Recording Period

AEs will be monitored and recorded in the subject's medical chart and research shadow chart from the time of first exposure to the investigational product avelumab, through 90 days following last dose of a study drug. AEs with an onset date prior to the first exposure to an investigational product will not be followed, except in the case of clinically significant worsening of the AE during the specified AE monitoring time frame.

9.7.1 Extended safety follow-up

- Given the potential risk for delayed immune-related toxicities, safety follow-up must be performed up to 90 days after the last dose of avelumab administration.
- The extended safety follow-up beyond 30 days after last avelumab administration may be performed either via a site visit or via a telephone call with subsequent site visit requested in case any concerns noted during the telephone call.

9.8 Adverse Event Reporting Requirements

9.8.1 Reporting to Product Manufacturer (EMD Serono)

The following reportable events must be submitted to EMD Serono within 2 business days or 3 calendar days (whichever comes first) using the applicable safety report form provided.

- Serious Adverse Events
- Exposure during Pregnancy or Breastfeeding (even if not associated with an adverse event)
- Occupational exposure (even if not associated with an adverse event)
- Potential drug-induced liver injury (Hy's Law cases): These events are considered important medical events and should be reported as SAEs.

Contact information for submission of reportable events to EMD Serono:

[contact]
OR
E-mail: [contact]

Specifying:

- PROTOCOL Number
- SUBJECT Number
- SITE Number/Sponsor-Investigator Name

9.8.2 SAE/ONSET DATE Reporting to IRB

The investigator or designee must report events to the FHCRC IRB in accordance with the policies of the IRB.

9.8.3 FDA Reporting Requirements

The Sponsor-Investigator assumes responsibility for IND safety reporting to the FDA, in accordance with regulations under 21 CFR 312.32.

Each SAE report will be evaluated by the Sponsor-Investigator to assess the seriousness of the event, the expectedness of the event, and the relationship to participation in the study. For regulatory reporting purposes, the Sponsor-Investigator will determine expectedness relating to avelumab and trabectedin using safety information specified in the avelumab investigator brochure and trabectedin FDA-approved package insert. An event will be classified as related if the Sponsor-Investigator determines that the event may be related to the study drug.

For determination of IND safety reporting, AE attribution will be assessed according to the suspected adverse reaction definition described in 21 CFR 312.32 as an AE for which there is a reasonable possibility that the drug caused the adverse event

where “reasonable possibility” means there is evidence to suggest a causal relationship between the drug and the AE. Suspected adverse reactions that are serious, related, and unexpected will be reported to the FDA as an IND safety report, in accordance with regulations under 21 CFR 312.32.

The Sponsor-Investigator will provide written notification of safety report to the FHCRC IRB per IRB policies.

All SAEs must be reported to EMD Serono from the time of study drug administration through completion of the study. SAEs that occur after the study-specific informed consent is signed but prior to the first dose of the investigational agent will be collected only if they are considered by the investigator to be causally related to the study required procedures. Probably related SAE will be reported to EMD Serono within 2 business days or 3 calendar days (whichever comes first) of investigator becoming aware.

10.0 MANAGEMENT OF TOXICITY AND COMPLICATIONS

10.1 Adverse Drug Reactions (ADRs) Related to Avelumab

Adverse Drug Reactions Requiring Avelumab Discontinuation or Modifications

The following ADR/AEs require permanent treatment discontinuation of avelumab if they are not expected toxicities of trabectedin and their management is not specifically outlined below:

Any Grade 4 ADR/AEs require treatment discontinuation with avelumab except for single laboratory values out of normal range that are unlikely related to study treatment as assessed by the Investigator, do not have any clinical correlate, and resolve or return to baseline within 7 days with adequate medical management

Any Grade 3 ADR/AEs require treatment discontinuation with avelumab except for any of the following:

- Transient (≤ 6 hours) Grade 3 flu-like symptoms or fever, which is controlled with medical management
- Transient (≤ 24 hours) Grade 3 fatigue, local reactions, headache, nausea, emesis that resolves to Grade ≤ 1
- Laboratory values out of normal range that may be related to trabectedin.
- Tumor flare phenomenon defined as local pain, irritation, or rash localized at sites of known or suspected tumor
- Change in ECOG PS to ≥ 3 that does not resolve to ≤ 2 within 14 days (infusions should not be given on the following cycle, if the ECOG PS is ≥ 3 on the day of study drug administration). Subjects may continue on study with ECOG PS ≤ 2 .

Any Grade 2 ADR/AE should be managed as follows:

- If a Grade 2 ADR/AE resolves to Grade ≤ 1 by the last day of the current week, treatment may continue.
- If a Grade 2 ADR/AE does not resolve to Grade ≤ 1 by the last day of the current week, infusions should not be given on the following week. If at the end of the following week the event has not resolved to Grade 1, the subject should permanently discontinue treatment with avelumab ADR/AE (except for hormone insufficiencies, that can be managed by replacement therapy; for these hormone insufficiencies, up to 2 subsequent doses may be omitted).

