4.0 TRIAL OVERVIEW

4.1 Study Design

4.1.1 Introduction

This is a Phase I/II, non-randomized, open-label, interventional study of avelumab combined with trabectedin for subjects with advanced L-type sarcoma.

The Phase I stage will evaluate trabectedin (1.5 mg/m²) combined with avelumab (800 mg flat dose). Dose reduction for the trabectedin therapy is permitted after the first cycle. Events which would require a dose reduction of trabectedin are outlined in Section 10, however additional dose reductions may be made at the discretion of the treating clinician down to a lowest possible dose of 1 mg/m². There will be no dose escalation or re-escalation of trabectedin.

4.1.2 Definition of dose limiting toxicity (DLT):

During the phase I portion of the protocol, a DLT will be defined as any grade 3 or higher adverse events, at least possibly-related to protocol therapy, which occur during the first 6 weeks of treatment, with the following specifications and limitations:

- Lab abnormalities that have no clinical sequelae (e.g. febrile neutropenia from low ANC, bleeding from thrombocytopenias etc.) and resolve to grade 1 or better within 7 days will not be considered a DLT.
- Any elevation in total bilirubin > 2x institutional ULN will be considered a DLT.
- Any elevation in AST and ALT over 8x institutional ULN will be considered a DLT.
- ANC <500/ μ L lasting 5 days or more will be considered a DLT.
- Platelets < 25,000/ μ L (grade 4 toxicity) lasting 5 days or more will be considered a DLT.
- Hemoglobin < 7.0 lasting 5 days or more will be considered a DLT.

Additionally, should any grade 5 toxicity (death) occur that is at least possibly-related to treatment (e.g. not easily otherwise explained; for example: a car accident), this will be considered a DLT. In the event of any grade 5 toxicity, enrollment will immediately be put on hold and a data safety monitoring board (DSMB) meeting will be requested immediately.

All clinically significant grade 3 or higher toxicities will be recorded and presented to the DSMB at scheduled meetings. Expected toxicities are those outlined in [Section 10](#). The DSMB will be specifically instructed to consider whether there are increased frequency of known toxicities and to make recommendations accordingly if appropriate. Section 10 summarizes criteria for required dose adjustments.

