8.2 On-Study Clinical Evaluations

A subject is considered on treatment on study day 1 when protocol defined therapy is first administered. Day 1 Avelumab is to be administered after all other protocol-specified pre-dose assessments have been performed during each visit that is required. Subjects will continue therapy until the completion of planned course of treatment, disease progression, or unacceptable AEs. Subjects should be instructed to immediately inform the treating investigator of an AEs. Clinical evaluations take place according to the Study Calendar (**Appendix C**).

Subjects on the Phase I portion of the trial should be evaluated as described below every week for the first 6 weeks and then on all weeks the subject is receiving treatment. Subjects on the Phase II portion of the study are evaluated as described below on weeks that they have treatment, prior to treatment. Every effort should be made to keep the schedule within \pm 3 days from the exact date the subject should be scheduled.

The study calendar will be managed in Weeks, with each dose of each drug being noted by a Cycle. For example, assuming there are no deviations from the planned schedule events, Week 1 will have Cycle 1 of avelumab and trabectedin. Week 3 will have Cycle 2 of avelumab, Week 4 will have Cycle 2 of trabectedin, Week 5 will have Cycle 3 of avelumab, Week 7 will have Cycle 4 of avelumab and Cycle 3 of trabectedin, etc. This may change based on dose delays or modifications. Weeks should be counted sequentially regardless of what number the dose of each agent is.

The following assessments will be performed on each treatment visit, unless otherwise specified:

- Tumor and Symptom-Directed Physical Exam and ECOG performance status evaluation
- Vitals Signs, including weight
- Urine or Serum Pregnancy Test – For Women of Childbearing Potential only (Only on days where avelumab is given as treatment, either alone or in combination with trabectedin. Screening pregnancy test must be serum pregnancy.)
- Hematology:
 - White blood cell (WBC) count with differential, absolute neutrophil count (ANC), red blood cell (RBC) count, hemoglobin, hematocrit, platelet count
- Clinical chemistry and liver function:
 - Sodium, chloride, potassium, glucose, blood urea nitrogen (BUN), creatinine, calcium, AST, ALT, total bilirubin, alkaline phosphatase, lactic acid dehydrogenase, total protein, albumin

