9.0 SAFETY

Monitoring for both acute and chronic toxicities will be evaluated at all study related visits and will be assessed by the Sponsor-Investigator. Toxicity information will be recorded and periodically reported to the the DSMB and EMD Serono. The Investigator will follow the guidelines below for treatment for toxicity. If a subject experiences toxicity, lab value abnormality, or other adverse event that is not described below, it will be up to the discretion of the treating Investigator if they want to delay study treatment and duration.

All adverse events and toxicity will be evaluated using NCI Common Terminology Criteria for Adverse Events (CTCAE) Version 5.0 as described in **Section 9.5**.

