9.1 Adverse Event

According to ICH guidelines for Good Clinical Practice; 21 CFR 312.32, IND Safety Reports; and ICH E2A, Definitions and Standards for Expedited Reporting, an adverse event is defined as follows:

An adverse event is any untoward medical occurrence in a clinical investigation subject administered a medicinal product and which does not necessarily have a causal relationship with this treatment. An AE can therefore be any unfavorable and unintended sign (including an abnormal laboratory finding), symptom, or disease temporally associated with the use of a medicinal product, whether or not considered related to the medicinal product.

Abnormal laboratory values for laboratory parameters specified in the study should not be recorded as an adverse event unless an intervention is required (repeat testing to confirm the abnormality is not considered intervention), the laboratory abnormality results in a serious adverse event or the adverse event results in study termination or interruption/discontinuation of study treatment.

Medical conditions present at screening (i.e., before the study treatment is administered) should be captured as baseline in the subject's research shadow chart. Medical conditions present at baseline that worsen in intensity or frequency during the treatment or post-treatment periods should be reported and recorded as adverse events.

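### Section 10.1 exempts a quickly resolving laboratory value judged unlikely related to treatment from permanent avelumab discontinuation at Grade 4, but has no matching exemption at Grade 3

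*Combined protocol and SAP*

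**What the plan says.** The lead-in of Section 10.1 requires permanent discontinuation of avelumab for the events it goes on to list, "if they are not expected toxicities of trabectedin and their management is not specifically outlined below". Separate rules by grade follow.

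- **Grade 4.** Every event stops avelumab, "except for single laboratory values out of normal range that are unlikely related to study treatment as assessed by the Investigator". Such a value must also have no clinical correlate and must resolve, or be back at baseline, within 7 days under medical management.
- **Grade 3.** "Any Grade 3 ADR/AEs require treatment discontinuation with avelumab except for any of the following". Five exceptions are listed: brief flu-like symptoms or fever; brief fatigue, local reactions, headache, nausea or emesis; "Laboratory values out of normal range that may be related to trabectedin"; tumor flare; and a change in performance status. Only the third concerns laboratory values.
- **Grade 2.** Treatment may continue if the event is down to Grade 1 or lower by the end of the current week. If not, the next week's infusions are omitted. Avelumab is stopped for good only if the event is still unresolved after that further week, with extra latitude for hormone insufficiencies.

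Three other sections bear on the point. Section 8.2 has blood chemistry drawn at each treatment visit, including "Sodium, chloride, potassium, glucose, blood urea nitrogen (BUN), creatinine, calcium". Section 9.1 says that an abnormal laboratory value is not recorded as an adverse event "unless an intervention is required (repeat testing to confirm the abnormality is not considered intervention"), or unless it leads to a serious event or to a change in treatment. Section 9.0 leaves an event "that is not described below, it will be up to the discretion of the treating Investigator" as to whether study treatment is delayed.

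**The concern.** The two laboratory exemptions turn on different attributions. Grade 4 excuses a value that study treatment probably did not cause. Grade 3 excuses a value that trabectedin may have caused. A value that neither drug caused meets the first and fails the second, so the milder event draws the harsher action.

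For the subject concerned, the stake is permanent loss of the investigational drug over a corrected laboratory value unconnected with it. For the trial, the stake is consistent conduct. An investigator who wants to keep such a subject on avelumab can do so within the text only by attributing the value to trabectedin. That is an unwelcome pressure on attribution where safety is a primary endpoint, although nothing in the documents shows that it would happen.

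**Working it through.** No arithmetic applies. The plan states no figure on this point and gives no rate for the values in question. The check is to take one event through the rules.

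**Test case.** A single potassium, sodium or calcium value that was treated, caused no symptoms, recovered within 7 days and was judged unlikely related to either drug.

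| Grade | Provision in Section 10.1 | Outcome for avelumab |
|---|---|---|
| 2 | Recovery by the end of the current week, or after one omitted week | Continues |
| 3 | Five exceptions, none of which fits | Permanent stop |
| 4 | Laboratory exemption fits on every condition | Continues |

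Grade 3 is the only one of the three grades at which this value has no recovery route.

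**Does another provision take the Grade 3 value out of the rule?**

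1. *Lead-in, expected trabectedin toxicity.* Section 10.3 lists leukopenia, transaminase, CK, bilirubin or alkaline phosphatase elevation and renal toxicity, among others. Sodium, potassium and calcium are not listed.
2. *Lead-in, management given below.* Table 2 in Section 10.2.2.4 has rows for liver tests and creatinine but none for electrolytes. Its row for other immune-related events deals with clinical signs or symptoms suggesting such an event, which a symptom-free value judged unlikely related is not.
3. *Not an adverse event.* Under Section 9.1 a value that needed correction is an adverse event. One that needed no intervention generally is not, which removes many values but not this one.
4. *Section heading.* The heading refers to reactions related to avelumab, but the rules speak of any ADR/AE. If values unlikely to be related were outside the section, the Grade 4 exemption would have nothing to exempt.
5. *Section 9.0 discretion.* It is confined to events that the later text does not describe, and it concerns delay of treatment. A rule that opens "Any Grade 3 ADR/AEs require treatment discontinuation with avelumab except for any of the following" does describe the event.

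None of the five removes the test case. Together they do remove most other laboratory values: those possibly due to trabectedin, those on the Section 10.3 list, liver and creatinine values managed in Table 2, and values that needed no intervention.

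**The case against.** The strongest reply is that attribution was meant to matter throughout. The heading of Section 10.1 names avelumab, and Section 9.6 counts an unlikely attribution as unrelated. Section 11.0, in its list of mandatory stops, names only Grade 4 or life-threatening toxicity attributable to study agent. If the rules for any Grade 2, 3 or 4 event reach everything, the discretion in Section 9.0 has little left to cover. On that reading an unrelated Grade 3 value never enters Section 10.1. This is a fair account of the likely intent, but it does not rescue the text. It makes the Grade 4 exemption in the same section redundant, and Section 11.0 does not override Section 10.1.

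Two narrower objections stand and limit the point. First, the Grade 3 laboratory exception is in other respects wider than the Grade 4 one: it does not require a single value, absence of symptoms or recovery within 7 days. Laboratory values in general are therefore not treated more harshly at Grade 3; only those with this attribution are. Second, vomiting and renal toxicity are expected with trabectedin, so a low potassium or sodium will often qualify as possibly due to it.

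A reader might also infer two stronger points that the documents do not support.

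- *That the DLT definition contradicts Section 10.1.* Section 4.1.2 says that laboratory abnormalities without sequelae that "resolve to grade 1 or better within 7 days will not be considered a DLT". But that definition takes in only events at least possibly related to therapy, so a value judged unlikely related never reaches it.
- *That a first Grade 3 diarrhea or rash rated only Possible must also end avelumab, whereas one rated Probable may resume.* This needs Table 2's reference to probably related toxicity to be read as a strict limit. Two other readings avoid the result: management of both events is outlined below in any case, or Section 9.6 makes a Possible event unrelated and so outside the heading. Nor can its frequency be bounded from Section 2.5, which counts treatment-related events, whereas this protocol classes Possible as unrelated.

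**Conclusion.** Section 10.1 is wrong as written for one narrow class of events, and the severity is minor. A single laboratory value judged unlikely related to study treatment, symptom-free and recovered within 7 days, is exempt from permanent avelumab discontinuation at Grade 4 and not at Grade 3.

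The conclusion assumes that Section 10.1 reaches adverse events whatever their attribution, as its wording and its own Grade 4 exemption imply. It also assumes that the value was recorded as an adverse event, mainly because it needed an intervention, and that the investigator does not consider trabectedin even a possible cause.

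The frequency is unknown and could be very low. A reader might infer that lost avelumab exposure would weaken the response-rate comparison, but the documents supply nothing from which to estimate that, and no effect on response rate or power is claimed.

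**What to change.** Add the Grade 4 laboratory exemption, word for word, as a further item in the Grade 3 exception list of Section 10.1. That is the clause "except for single laboratory values out of normal range that are unlikely related to study treatment as assessed by the Investigator", without its first two words, together with the two conditions that follow it there on absence of a clinical correlate and recovery within 7 days. Leave the existing trabectedin laboratory exception and Table 2 unchanged.

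The cost is one added line in a protocol amendment, with no further patients, procedures or data collection. For these values it gives Grade 3 no more latitude than Grade 4 already has.

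### Section 10.1 lists an ECOG stopping criterion among the exceptions to the Grade 3 avelumab stop, so as written it exempts the decline that does not recover

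*Combined protocol and SAP*

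**What the plan says.** Section 10.1 opens by naming events that require permanent discontinuation of avelumab, limited to those that qualify "if they are not expected toxicities of trabectedin and their management is not specifically outlined below". Under that lead-in come rules by grade.

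- **Grade 4.** Avelumab stops, except for isolated laboratory values that are unlikely to be related, have no clinical correlate and "resolve or return to baseline within 7 days with adequate medical management".
- **Grade 3.** "Any Grade 3 ADR/AEs require treatment discontinuation with avelumab except for any of the following". Five bullets follow. Two are time-limited in the usual way: "Grade 3 flu-like symptoms or fever, which is controlled with medical management", if it lasts no more than 6 hours, and "Grade 3 fatigue, local reactions, headache, nausea, emesis that resolves to Grade ≤ 1", if it lasts no more than 24 hours. The fifth is "Change in ECOG PS to ≥ 3 that does not resolve to ≤ 2 within 14 days". It carries a parenthesis, "infusions should not be given on the following cycle, if the ECOG PS is ≥ 3 on the day of study drug administration", and ends "Subjects may continue on study with ECOG PS ≤ 2".
- **Grade 2.** An event not back to Grade 1 by the end of its week leads to a hold. If it is still unresolved at the end of the next week, avelumab stops permanently, with an allowance for hormone insufficiencies.

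Section 8.2 has ECOG performance status assessed at each treatment visit.

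**The concern.** The fifth bullet is worded as a reason to stop but is placed in a list of reasons not to stop. The site is left with a permanent-discontinuation rule whose literal direction is opposite to what the rest of the bullet implies. At stake is who stops avelumab for good after a fall to PS 3 or worse, and who may go back on it. ECOG status is checked at every treatment visit, so the rule comes into play whenever an in-scope decline occurs. A monitor who applied the literal wording could query either action.

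**Working it through.** No arithmetic is involved, and the plan states no figure to reproduce. The check sets the text of section 10.1 side by side and then looks for a correction elsewhere.

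**Step 1: the literal rule, case by case.** The structure is: Grade 3 event, therefore stop, unless listed.

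| Fall to PS ≥ 3 | Listed as an exception? | Literal result | Result implied by the closing sentence |
|---|---|---|---|
| Not back to ≤ 2 within 14 days | Yes | Exempt from the stop | Does not qualify to continue |
| Back to ≤ 2 within 14 days | No | Stop not lifted | May continue |

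The two columns disagree in both rows.

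**Step 2: the other timed exceptions in 10.1.**

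| Exception | Limit | Event that is spared |
|---|---|---|
| Grade 4 laboratory value | 7 days | The one that resolves in time |
| Grade 3 flu-like symptoms or fever | 6 hours | The one that ends in time |
| Grade 3 fatigue, nausea and similar | 24 hours | The one that ends in time |
| ECOG decline | 14 days | The one that does **not** resolve in time |

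Three of the four point one way. The ECOG bullet is the only one that points the other way.

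**Step 3: the Grade 2 rule.** Failure to resolve is there a reason for permanent discontinuation. As written, an unresolved Grade 2 event must end avelumab, while an unresolved fall to PS 3 or worse is excused from the stricter Grade 3 rule. The plan gives no reason for that ordering.

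**Step 4: is it corrected elsewhere?** Section 11.0 lists general grounds for stopping treatment and has no ECOG criterion. Section 4.1.4 mentions ECOG decline only as a condition for treating on while progression is being confirmed. The immune-related event tables in 10.2.2.4 contain no ECOG rule. None of these restates or repairs the bullet.

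**Step 5: what still stops the non-recovering subject?**

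- No infusion is given while PS is 3 or worse on the dosing day (10.1).
- The bullet exempts the ECOG change, not its cause. An in-scope Grade 3 event behind the decline still ends avelumab, unless it meets one of the other exceptions.
- An in-scope Grade 2 event that fails to resolve ends avelumab.
- Progression ends treatment (11.0), and an investigator may stop treatment at discretion.

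The gap is therefore persistent PS 3 or worse with no other stopping event. That subject is held from dosing, but no rule says when the hold becomes permanent. Avelumab is given every 2 weeks (4.1.3), so 14 days is one dosing interval. That fits a sequence of hold, reassess and decide, but the decision is written the wrong way round.

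**Step 6: scope.** The lead-in removes expected trabectedin toxicities and events managed elsewhere in the section. Section 10.3 lists nine expected toxicities. Four of them (malaise, infection or sepsis, fatigue, nausea or vomiting) are, in my judgement, plausible causes of a performance-status decline, and they fall outside this rule.

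**The case against.** The strongest reply is that the bullet would be correct as worded if it sat directly under the lead-in, level with the Grade 4 and Grade 3 rules, and that its place in the exception list could be an indentation lost when the PDF was read. This cannot be excluded, but it is not shown. Nested bullets survive in other lists of the same document (section 8.2, for example), and here the bullet stands at the same level as the four exceptions above it. If a criterion was misplaced in the protocol itself, the need for repair is the same.

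A second reply is that ECOG status is not a CTCAE grade. Adverse events are graded by CTCAE (9.5), and 9.4 asks for the diagnosis to be recorded and not its symptoms. The decision will often turn on the underlying event. That stands, and it narrows the practical effect.

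Three stronger readings are tempting, and the documents do not support them.

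- *A subject at PS 3 or worse keeps receiving avelumab.* The dosing-day hold prevents this.
- *The non-recovering subject faces only a hold or investigator discretion.* Step 5 lists other mandatory stops.
- *The recovered subject must stop.* The closing sentence gives specific permission to continue. The fault is that the exception list does not say the same.

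**Conclusion.** Wrong as written. The bullet's position and wording contradict each other, and section 10.1 alone is enough to show it. The conclusion rests on taking the list level as it appears, and on reading the closing sentence and the parallel exceptions as evidence of intent.

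The size is small. The number of subjects affected cannot be estimated from the documents and is probably low. The scope is narrow, and the hold limits harm. Sample size, power and the response analysis do not depend on it. Two things are missing: a permanent ECOG-based stop for persistent PS 3 or worse without another stopping event, and an unambiguous statement that the recovered subject may resume. It should still be corrected, because this is an operative safety rule and staff should not have to read it against its wording.

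**What to change.** Move the bullet out of the Grade 3 exception list so that it stands as its own discontinuation criterion under the existing lead-in of 10.1. Keep that lead-in's two scope limits, the dosing-day hold and the closing sentence. Do not add a separate discontinuation sentence without those limits.

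If a Grade 3 exception is also wanted, word it for the decline to PS 3 or worse that resolves to PS 2 or better within 14 days. Deleting 'not' from the present bullet is not an equivalent repair. It only removes an exemption, so the non-recovering subject would have to stop only if the decline itself counted as a Grade 3 event.

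The cost is a line or two of amendment text. ECOG status is already collected at each treatment visit, so visits, data collection and sample size do not change.
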